
Active treatments are common and a significant source of symptom burden and poor HRQoL. Despite the utility of active surveillance (AS) in low risk PC, AS remains underused (i.e., ~12% of eligible patients). ^{45, 46} Independent of PC risk, use of active treatment increased about 10% from 2004- 2012 (~70% of localized cases receive active treatment). ^{47,48} Treatment related symptom burden (i.e., sexual & urinary dysfunction), pain, fatigue and compromised HRQoL (e.g., physical, social/family, emotional & functional well being) are a persistent source of concern and bother. ^{3, 4, 49} Years after treatment, 82% of surgery patients and 50% of radiation patients remain impotent (ED), and 68% report poor urinary control. ^{50, 51}The impact of ED on HRQoL is significant, affecting sexual interest and desire, relationship quality, body image, and masculinity and self-esteem, with up to 85% of men with ED reporting significant levels of psychological distress. ^{52,53,54,55,56}

Psychosocial interventions reduce symptom burden and improve HRQoL in cancer survivors. Psychosocial interventions facilitate adaptation and favorably impact mechanisms known to reduce symptom burden and improve HRQoL in cancer survivors. ⁵⁷⁻⁵⁸ In BC and PC, we have shown that a cognitive behavioral therapy (CBT) group-based stress and self-management psychosocial intervention (CBSM)^{59,60} reduced symptom burden, and improved HRQoL, with stress management skills mediating these effects. ⁵⁷ However, most of this work has focused on non-Hispanic whites (NHWs), with some attention to Hispanics but with extremely limited consideration of Spanish speakers or Hispanic cultural processes.

PC Survivorship Disparities. African Americans (AAs) and Hispanic/Latinos (Hispanics hereafter) treated for

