What is the link between inflammation, symptom burden, HROoL and overall health in PC survivors? Psychosocial stress can impact symptom burden and HRQoL via neuroendocrine and pro- inflammatory mechanisms. ¹²⁸ In PC, higher C-reactive protein (CRP), IL-6, IL-8 and TNF-α are associated with ED^{129,130,131} independent of risk factors. Inflammatory states can influence recovery from PC treatment by interfering with the recovery of pathways and tissue necessary for adequate sexual and urinary functioning. 132,133 For example, TNFα reduces endothelial nitric oxide (NO) synthase thus interfering with erectile function. Inflammatory cytokines are also implicated in fatigue and in turn, fatigue is associated with distress and depression, and poor HRQoL. 134,135 In PC, avoidant coping is associated with disrupted diurnal cortisol, ¹³² while inflammation is related to greater fatigue. 136 Further, inflammation has also been implicated in bladder dysfunction. 137 In our preliminary work, we found that (a) CBSM improved diurnal cortisol regulation, and (b) improvements in cortisol regulation were associated with reductions in pain and better physical functioning. We have documented strong associations between inflammatory cytokines (IL-1, IL-6 & TNF) and sexual and urinary dysfunction, depression, pain and fatigue in PC. 138 Thus, regulation of glucocorticoid receptor sensitivity and inflammatory pathways via psychosocial mechanisms (e.g., stress reduction, mood) may provide one of several biological mechanisms of how stress, anxiety and other emotional/cognitive processes affect symptom burden and HROoL. Furthermore, cardiovascular disease (CVD; e.g., heart attacks, congestive heart failure, vascular disease, stroke) is among the leading causes of death in localized PC. ¹³⁹ Inflammation is a significant contributor to heart disease, and it is well established that inflammatory responses can exacerbate atherosclerotic processes. 140,141,142,143 As we expect that stress management will reduce inflammation, we will have the unique opportunity to evaluate how such changes in inflammatory responses are favorably associated with markers of cardiometabolic health including blood pressure and fasting glucose. 144,145,146

Design and Procedures:

Participants:

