This project will involve voluntary participation of approximately 200 men treated for a primary diagnosis of localized prostate cancer (PC; Stages1-3, NO, MO) within minimum of 1 month and maximum of -96 months with no evidence of disease recurrence. All participants will be self-identified Hispanics/Latinos (hereafter referred to as Hispanic) of any racial category who speak Spanish or are bilingual but express interest in a Spanish intervention program. We anticipate that about 50% of the population in our target communities is Spanish monolingual or is not proficient in English as these communities have large concentrations of foreign-born Hispanics. Nonetheless, we will also involve participants who are bilingual and agree to participate in a Spanish psychosocial intervention.

Inclusion Criteria:

- ≥ 18 years of age;
- Hispanic/Latino self-identification;

- Study #: 20170656 Effective Date: 8/14/2025
- Spanish speakers (including bilinguals who express interest in a Spanish-based psychosocial intervention);
- Primary diagnosis of localized Prostate Cancer (Stages 1-3, N0, M0);
- Surgical or radiation treatment (e.g., external beam, brachytherapy, proton) within minimum of 1 month and maximum of 96-months;
- Some patients with prior inpatient psychiatric treatment for severe mental illness or overt signs of severe psychopathology (e.g., psychosis) may be enrolled, per P.I. discretion, based on a case-by-case review;
- Willingness to be randomized and followed for approximately 12 months.

Exclusion Criteria:

- History of non-skin cancer within the last 2 years
- Prior inpatient psychiatric treatment for severe mental illness or overt signs of severe psychopathology (e.g., psychosis) within the past six months, as these conditions can interfere with adequate participation in our experimental conditions may be exclusionary, per P.I. discretion, based on a case-by-case review;
- Active alcohol dependence within the past six months may be exclusionary, per P.I. discretion, based on a case-by-case review;
- Active substance dependence within the past six months may be exclusionary, per P.I. discretion, based on a case-by-case review; and
- Acute or chronic immune system medical conditions, medications or conditions that impact immune and endocrine function (e.g., CFS, Lupus, rheumatoid arthritis, Hepatitis C, or immunosuppressive treatment requiring conditions), per P.I discretion, based on a case-by-case review.

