We conduct genome-wide transcriptional profiling of monocytes, the cells that initiate and maintain most inflammatory responses. 160,161 For in-person blood collection 10-ml of blood are drawn into BD Cell-Separator Tubes. After PBMCs have been isolated through centrifugation, they are labeled with immunomagnetic beads against CD14, ¹⁶² a surface marker specific to monocytes. By passing the labeled cell suspensions through Mitenyi's autoMACS instrument, we can acquire a relatively pure (~90%) population of monocytes through positive selection. The acquired cells will then be lysed and stabilized (RNeasy Mini-Kits), 163 and frozen at -80°C until shipment to UCLA for transcriptome profiling assay. Again, both [name] and [name]'s lab have successfully implemented this protocol in previous collaborations with [name]. 157 [name] lab at UCLA will extract total RNA using PCR-clean and RNAse-free techniques, and check sample quantity and quality with NanoDrop 1000 and Agilent Bioanalyzer 2100 instruments. 150ng of the RNA will be transformed to fluorescent cRNA, hybridized to Illumina Human HT-12 bead arrays, and scanned on a Illumina iScan reader. Raw expression values will be quantile-normalized and log-2 transformed for statistical analysis, and the pool of differentially expressed genes will be identified by Linear Mixed Models that compare CBSM and C-CBSM groups, net of demographic and biobehavioral confounders (e.g. age, BMI, co-morbidities and disease-relevant confounders such as time of treatment, time since treatment). Differentially expressed genes are defined as those showing ≥1.5-fold difference between groups and a transcript-level false discovery rate of < 5% (using standard Benjamini & Hochberg stepdown analysis. 164 Up to 10 differentially expressed genes will be re-verified using quantitative RT-PCR with TaqMan gene expression assays (Applied Biosystems Inc.), a one-step enzyme system, 165 and manufacturer's specified thermal cycling protocol on a iCycler real-time PCR instrument (BioRad Inc.). To identify transcription control pathways underlying differential gene expression, we use a 2-sample variant of the Transcription Element Listening System (TELiS). 166 TELiS quantifies the prevalence of transcription factor-binding motifs within promoters of differentially expressed genes. Analyses focus on 3 transcription factors (TFs) by which C-CBSM could affect monocyte inflammatory activity: NF□B, the major pro- inflammatory TF; CREB, a TF that conveys adrenergic signals to monocytes, and whose activity reflects the amount of SNS signal reaching these cells' genome; and glucocorticoid receptor, a TF that propagates cortisol's anti-inflammatory signals within monocytes and, like CREB, indexes how much hormone signal these cells are registering. For the remote blood collection that is collected via dried blood samples (DBS) we will use standard DBS collection procedures that have been well validated and used by our research team (i.e., [name]). 200, 201 Briefly, the samples are collected by pricking the tip of the middle digit with a sterile disposable lancet, and then allowing drops of blood to wick onto filter paper cards Total RNA will be extracted from DBS samples by cutting 2-4 blood spots from the 5-spot filter paper for each sample (using a separate razor blade for each sample to prevent contamination), depositing all filter paper spots from each sample into 370 µL of RLT in an RNAse-free sterile 1.5 ml microcentrifuge tube, incubating the tube for 30 min at 37° C with agitation (1000 rpm), transferring tube contents (including filter paper) into a QIAshredder column for 60 sec microcentrifugation at maximum speed, after which the 360 µL of remaining RLT was processed through the QIAcube nucleic acid extraction system using RNeasy Micro Kit reagents, the manufacturer's standard operating protocol (including DNAse treatment), and a 20 µL elution volume. DBS samples are highly stable, can sit overnight at room temperature and can be mailed for subsequent storage in a -80 freezer. Samples will be stored/batched at [name] lab and mailed to Co-I [name]'s lab at Northwestern

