Participants will be randomized by cluster randomization (C-CBSM or CBSM) to balance treatment type across conditions. We project to retain 140 participants at our 12-months post-intervention assessment visit (T4). All participants will be asked to participate in 10-weekly 90-minute in person sessions targeting CBT based skills for managing stress and self-management in one of two experimental conditions—a linguistically translated (Spanish) and culturally adapted cognitive behavioral stress and self-management (CBSM) condition (i.e., C-CBSM) or in a standard version of CBSM that is only linguistically translated (CBSM). Following the baseline visit (T1, pre C-CBSM or CBSM), participants are randomly assigned into one of our experimental or control condition groups.

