To Test Exploratory Hypotheses. Aim 3: For Hypotheses 3, the linear mixed model will include fixed effects for the experimental group (C-CBSM vs. CBSM) and observation time (T1-T4), and random effect for person with a compound symmetry covariance structure for the repeated residuals within person. A group by time interaction and post-hoc tests on this model effect will indicate whether and how the time course of the dependent variable differs between the groups. Hypotheses 1-3 will all be analyzed in a similar manner using the outcome measures described in sections C.6.c (Primary Outcomes), C.6.d (Intervention Targets) and C.6.e (Inflammation) respectively. These measures include markers of symptom burden, systemic inflammation, and cytokine production following cellular activation with TLR ligands. Data from gene expression profiling are analyzed using advanced bioinformatics techniques, and described in C.6.e, and as reported previously by Antoni et al.¹²⁴ As each outcome across the different study hypotheses have been carefully selected to address a priori hypotheses, no adjustment for testing of multiple outcomes will be made. However, within the analysis of a specific outcome, Tukey or Bonferroni adjustment will be made for the multiple tests across different time points. The power calculation below adjusts for this multiplicity. Aims 4a-4c: These hypotheses involve tests of proposed mediators of C-CBSM's effect on our primary outcomes. To test mediation with LGM, individual change trajectory (in each outcome of interest) is characterized by an intercept and a slope factor. The overall pattern of change (e.g., linear, quadratic, etc., as informed by analyses for Aims 1-3) for the whole group can be specified by a particular set of coefficients associated with the slope factor. First, we will specify a growth curve model for all participants with an intercept factor representing our outcome of interest at baseline, and the slope factor reflecting the change trajectory in our outcome measure from T1 to T4. For example, to test that increased stress management skills (e.g., MOCS) in the C-CBSM group accounts for reductions in symptom burden (e.g., EPIC-S), we will first test a LGM model without the stress management skills (the mediator) and then test the model with change in stress management skills from T1 to T4. In the model without the stress management skills, we expect that group assignment is not related to baseline symptom burden, but that group assignment will be related to a greater negative change (reduction) in symptom burden scores. In the next step, we will add stress management skills and expect that after adding this mediator in the model, the path between group assignment and symptom burden slope will become non-significant, while the path between the mediator and symptom burden slope is significant thus suggesting mediation. This approach will be applied to test all mediation models in hypotheses 4a-4c. 191,192 Aim 5a-5b: To evaluate moderators and mechanistic pathways of C-CBSM's effects, we will use LMM and latent variable mediation models. For Hypothesis 5a, we will test moderation by including interaction terms between group assignment (C-CBSM vs. CBSM) and each moderator of interest (e.g., SES, acculturation, Hispanic ancestry, treatment type) within the LMM framework. These models will include fixed effects for group, time (T1-T4), the moderator, and the group × moderator and group × time × moderator interactions. A significant three-way interaction (group × time × moderator) will indicate that change in the outcome (e.g., inflammation, symptom burden, HRQoL) over time differs by both treatment group and the level of the moderator. Post-hoc comparisons will clarify the nature of the moderation effects across timepoints. For Hypothesis 5b, we will test whether improvements in cardiometabolic markers (e.g., lipids, fasting glucose, blood pressure) in the C-CBSM group are mediated by reductions in inflammation using SEM. Parallel process LGMs will estimate trajectories for inflammatory markers and cardiometabolic outcomes across time. The indirect effect from group assignment to cardiometabolic outcome slope via inflammation slope will be tested. This approach allows for simultaneous modeling of changes over time, capturing both within- and between-subject effects. Model fit will be evaluated using standard criteria (CFI > .95, RMSEA ≤ .05, SRMR < .08), and significance of indirect effects will be tested using bias-corrected bootstrapped confidence intervals.

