0.81 and 0.42 respectively. With greater effect sizes anticipated in the proposed study, the sample size of at least 100 per arm has sufficient power to detect differences even after adjusting for the analysis of change from baseline to post-intervention time points. Power for C-CBSM's effect on down regulation of inflammatory genes are based on Antoni et al.¹²⁴ study which indicated that the observed effect size was one standard deviation in a sample size of 45 in the experimental condition. Glucocorticoid receptor sensitivity demonstrated similar effects. With a T4 sample size of 100 in the C-CBSM group, effect sizes of 0.48 standard deviations are detectable with 80% power at a 2-tailed Type I error rate of 1%, so that expected effects will be detectable with sufficient power. While pilot data are not available for all outcome measures, the constant in the power calculation regardless of the outcome is the effect size expressed in terms of standard deviations, which is 0.40 or 0.49 depending on whether the Type I error rate is 5% or 1%.

Covariates, Cohort Effects, Intent to Treat & Missing Data. A number of variables (e.g., SES, disease factors) will be considered as possible covariates. These putative confounds will be entered as covariates if correlated with our outcomes (at p<.10). Random assignment should render groups equivalent on covariates and this will be verified post-hoc. We will test differences among cohorts who have completed our conditions by doing an ANOVA within each condition with k levels of cohort. If we find a cohort with differential outcomes (significant Condition x Cohort x Time interaction), we will conduct a Group x Time interaction tested within each cohort, and a Cohort x Time interaction tested within assignment. We have never observed a significant cohort effect in prior CBSM work. We will also use an intent-to-treat approach in that all participants will be retained in the analysis, including those with missing data at time points by using full information maximum likelihood (FIML) estimation. FIML, a recommended state-of-the-art method, 197,198 uses all available data for each participant and provides unbiased estimates of parameters when the data are missing at random.

Cost to the Participants:

There will be no cost to the participants for taking part in this study. All expenses related to the study activities, including laboratory tests done and lab materials.

Risk and Benefits:

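### Time since treatment (1 to 96 months at entry) is not pre-specified in the Hypothesis 1 models, and the p<.10 covariate rule, read as a main effect, does nothing for the group-by-time contrast

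*Combined protocol and SAP*

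**What the plan says.** - **Entry window.** The Participants section admits men treated "within minimum of 1 month and maximum of -96 months" earlier. The minus sign is a typographical slip; the inclusion criteria give a maximum of 96 months.
- **Recovery.** The Background section on inflammation and symptom burden treats function as something that recovers: "Inflammatory states can influence recovery from PC treatment by interfering with the recovery of pathways and tissue necessary for adequate sexual and urinary functioning".
- **Primary test.** Test of Study Hypotheses specifies linear mixed models with categorical time. The paragraph To Test Exploratory Hypotheses lists group, time and a person effect, then says "A group by time interaction and post-hoc tests on this model effect will indicate whether and how the time course" differs between groups. It states that Hypotheses 1 to 3 are handled alike.
- **Adjustment.** The section Covariates, Cohort Effects, Intent to Treat & Missing Data says "A number of variables (e.g., SES, disease factors) will be considered as possible covariates" and then "These putative confounds will be entered as covariates if correlated with our outcomes (at p<.10". It expects randomisation to balance covariates and will check this afterwards, with no stated action if balance fails.
- **Where time since treatment appears.** For adjustment it is named only in the gene-expression model (Genomic Level), among "disease-relevant confounders such as time of treatment, time since treatment".
- **Allocation.** "Participants will be randomized by cluster randomization (C-CBSM or CBSM) to balance treatment type across conditions". Time since treatment is not mentioned as a balancing factor.

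**The concern.** The outcomes at issue are change in EPIC sexual and urinary scores. A man one month out may improve a good deal over the following year whichever programme he attends; a man eight years out probably will not. That spread in recovery adds noise to change. If by chance one arm holds more recently treated men, it also shifts the estimated difference in change.

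A sensible covariate model would absorb both. The stated rule appears not to:

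- It names no form for the covariate, and the natural reading of entering a variable as a covariate is a main effect. Where the plan wants interactions with time it writes them out, as in the moderator models for Hypothesis 5a, and the moderators listed there do not include time since treatment.
- It screens on correlation with the outcomes without saying whether that means level or change. Recovery acts on change.
- If the form is truly open, a choice in the primary model is left until the data can be seen.

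**Working it through.** **1. The plan's own figure.** Power Analyses gives detectable effects, as difference in mean change over SD of change, of 0.40 at 5% and 0.49 at 1%, with 100 per arm and 80% power.

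n per arm = 2(z₁₋α/₂ + z₀.₈₀)²/d²

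- 5%: 2(1.960 + 0.842)²/0.40² = 98.1, so 99; power at 100 per arm is 0.807.
- 1%: 2(2.576 + 0.842)²/0.49² = 97.3, so 98; power at 100 per arm is 0.813.

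Both figures reproduce.

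**2. Why a main effect does nothing.** For man i in group g at visit t, with baseline covariate x:

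Y(i,t) = μ(t) + γ(t)g + βx + b(i) + e(i,t)

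The change from T1 to T4 is [μ(4) − μ(1)] + [γ(4) − γ(1)]g + e(i,4) − e(i,1). The term βx cancels. If the slope may vary by visit, [β(4) − β(1)]x stays in the change and can be adjusted for.

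**3. Numerical check.** A random-intercept mixed model was fitted to simulated T1–T4 data. Group × visit estimates at T2, T3 and T4:

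| Model | Complete data | SE |
|---|---|---|
| No covariate | −0.0865, 0.0775, −0.1904 | 0.1456 |
| Main effect | −0.0865, 0.0775, −0.1904 | 0.1456 |
| Covariate × visit | −0.0734, 0.1017, −0.1487 | 0.1432 |

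With 30% dropout the main effect moved the T3 and T4 estimates by about 0.004 (0.3632 to 0.3597; 0.0101 to 0.0065).

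**4. Is there bias?** Individuals were randomised 4,000 times under each of three recovery scenarios. Without covariate × visit, the mean error ran from −0.004 to 0.001 and type I error from 0.054 to 0.058. With it, type I error was 0.052 to 0.057. Simulation error is about 0.003. So there is no systematic bias.

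**5. Size, under assumptions.** The documents give no recovery curve and no distribution of entry times. Assume recovery over 12 months for a man entering at t₀ months is A[exp(−t₀/τ) − exp(−(t₀+12)/τ)], with A = 1 to 3 residual SDs of change and τ = 6 to 12 months. Entry is either uniform over 1–96 months, or skewed to recent treatment (exponential, scale 24 months, cut to the window). With s the SD of recovery across men and residual variance 1:

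- share of change variance R² = s²/(1 + s²)
- SD of chance imbalance = √(2/100) × √R²
- power uses d = 0.40/√(1 − R²)

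| Entry, A, τ | s | R² | Imbalance SD | Power at 100 per arm | n per arm for 80% |
|---|---|---|---|---|---|
| Uniform, 1, 6 | 0.122 | 0.015 | 0.017 | 0.813 | 97 |
| Uniform, 3, 9 | 0.387 | 0.131 | 0.051 | 0.858 | 86 |
| Recent, 1, 12 | 0.173 | 0.029 | 0.024 | 0.819 | 96 |
| Recent, 2, 6 | 0.392 | 0.133 | 0.052 | 0.860 | 86 |
| Recent, 3, 6 | 0.588 | 0.257 | 0.072 | 0.907 | 73 |

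The first and last rows are the extremes of the grid. Power without the interaction is 0.807 throughout. These gains assume the covariate captures recovery in full; log months would capture somewhat less.

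**6. At the projected T4 sample.** The Randomization Protocol projects 140 men at T4. At 70 per arm, power for 0.40 at 5% is 0.66. With R² = 0.015 to 0.257, d becomes 0.403 to 0.464, and d√35 − 1.96 = 0.42 to 0.79, which gives power of 0.66 to 0.78. The imbalance SD grows by √(100/70) = 1.20, to about 0.02 to 0.09.

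**The case against.** The strongest reply is that randomisation already deals with this. Recovery common to both arms goes into the time effect and cancels, and the standard error already covers chance imbalance. That stands. A reader might infer that natural recovery will be mistaken for an effect of C-CBSM; the documents and step 4 do not support that as a systematic effect.

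A reader might also infer that the plan restricts covariates to main effects. It does not say so; it leaves the form unstated. The finding is that the form is unspecified and that the natural reading is ineffective.

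The sizes rest on assumed curves. The protocol also calls side effects chronic and persistent, which points to the lower end. The figure that "82% of surgery patients and 50% of radiation patients remain impotent (ED" describes levels years after treatment, not different courses over follow-up, and allocation already aims to balance treatment type. So the case for treatment type × visit is weaker than for time since treatment.

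It is tempting to add that allocating whole groups makes the imbalance worse. It could: with groups of 4 to 8 and an assumed intraclass correlation of entry times of 0.05 to 0.20, √(1 + (m − 1)ρ) runs from 1.07 (m = 4, ρ = 0.05) to 1.55 (m = 8, ρ = 0.20). No such correlation is given, so this is a possibility, not a finding.

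What survives is that disease factors as candidate covariates, plus a post-hoc balance check, do not commit the primary model to any term that can act on change.

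**Conclusion.** The point holds as one of precision and pre-specification. Time since treatment spans 1 to 96 months, is not named for the Hypothesis 1 models, is not a stated balancing factor, and would enter, if at all, through a data-driven screen in a form that leaves the group × time contrast untouched.

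The validity of the randomised comparison is not in question. The cost runs from negligible to moderate: a typical (1-SD) chance shift of 0.02 to 0.07 SD against a target of 0.40, and forgone power of between less than 0.01 and 0.10 at 100 per arm. The algebra needs no assumption beyond complete data; the sizes depend wholly on the assumed recovery curves and entry distributions. This is a cheap improvement worth making, not a flaw that undermines the trial.

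**What to change.** In To Test Exploratory Hypotheses (which sets the model for Hypotheses 1 to 3) and in Covariates, Cohort Effects, Intent to Treat & Missing Data, state that the Hypothesis 1 models include time since treatment, for example log months at T1, and its interaction with visit, for every man and whatever the result of the p<.10 screen. Treatment type × visit may be added on the same basis, with less expected gain. For any other covariate, say whether it enters as a main effect or crossed with visit.

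The cost is wording and a few parameters. With four visits, one continuous covariate adds 1 + 3 = 4, and each treatment-type indicator adds 4 more. Eligibility already requires the timing of treatment, and treatment type is already collected, so no new data or participants are needed.
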